There will be a "STOPPING RULE" for further individual participation in the study for any of the following criteria: withdrawal of consent, diffuse rash or anaphylaxis reaction to medication (requires confirmation by house officer), hypotension requiring delivery or medication such as ephedrine, or development of any obstetrical outcomes that would normally preclude tocolysis (development of ruptured membranes, development of chorioamnionitis, development of preeclampsia/gestational hypertension, development of bleeding suspicious for abruption, cervical dilatation of 6 cm or more or fetal death), or if a decision is made to either deliver the patient or to use regional anesthesia.

Women without further cervical change after monitoring on Labor and Delivery will be admitted to the antepartum unit for surveillance until approximately 34 weeks' gestation and completion of the full course of corticosteroids, although the provider will determine when it is safe for the patient to be discharged. This is our current practice in such women and is not a study procedure. Discharge can be affected by whether the patient is considered stable (is she contracting again?), if her cervical exam has changed (if her cervix has increased dilatation, particularly to 4 cm or more, she may not be considered safe for discharge) and if she is receiving any other interventions. We will avoid creating an expectation that by participating in this study, then an exact or particular discharge date is assured. Some patients choose to leave earlier (usually due to family obligations) despite the recommendation to stay until 34 weeks' gestation. Women who are discharged from the antepartum unit will be followed-up in the OB Complications Clinic of Parkland Hospital weekly until delivery. This method of outpatient follow-up for patients after discharge from the antepartum unit is also our routine and is not a study specific procedure.

2. *You may include tables, figures and/or flow diagrams if necessary to clarify highly complex studies.*

N/A

3. *Indicate the timing of all study procedures and the anticipated duration of the subject's involvement.*

Study participants involvement in study related procedures will last 48 hours.

4. *As applicable, include the amount and blood to be drawn, tissue samples to be collected, radiation exposure, questionnaires, or other interventions.*

No additional blood, tissue, imaging studies, questionnaires or other interventions are planned.

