**Exclusion criteria:**

Oppose inclusion criteria:

- Multifetal gestation
- Less than 28 weeks' gestation
- 34 or more weeks' gestation
- Ruptured membranes

• More than 4 cm dilated  
Corticosteroids contraindicated:

- Previously received a course of corticosteroids for fetal lung maturation

Tocolysis contraindicated:

- Low amniotic fluid (oligohydramnios)
- Fetal growth restriction
- Chorioamnionitis or temperature of at least 38.0 degrees Celsius
- Fetal death
- Preeclampsia
- Suspected placental abruption or placenta previa
- Lethal fetal malformation or amniotic fluid index at least 35

Nifedipine contraindicated:

- Systolic BP < 90 mmHg or diastolic BP < 50 mmHg
- Baseline tachycardia (pulse >120 after 2 consecutive measurements 30 minutes apart)
- Chronic hypertension treated with antihypertensives in pregnancy
- Seizure disorder or HIV\*
- Women who have received progesterone therapy in the 2nd or 3rd trimester
- Maternal allergy to nifedipine
- Known maternal cardiac disease

\* See July 2013 FDA warning regarding nifedipine and phenytoin, also several protease inhibitors are strong inhibitors of metabolizing enzyme CYP3A4

2. *Include situations or conditions, unknown at the time of enrollment that might cause a screening failure.*

No situations known.

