### **Summary of Sections 66.0 and 67.0 of the Smart Form for the Data Safety Monitoring Plan and Committee**

*Who comprises the Data Safety Monitoring Committee (DSMC)?*

The DSMC is composed of [name], PhD, Professor and Statistician within the Department of Obstetrics and Gynecology, as well as two faculty physicians from the Department of Obstetrics and Gynecology not participating in the study ([name] and [name]).

*When will the DSMC meet:*

The DSMC will meet at least annually during the projected 4 year duration of the study. Additionally, after accrual of 75 patients (half of the planned 150 patients for recruitment), an interim analysis will be performed.

*What will be analyzed by the DSMC?*

The DSMC will monitor study accrual rate, study attrition including participant withdrawals/dropouts, patterns of AEs and/or unanticipated events, patterns of protocol deviations and/or violations and changes in risk/benefit. Efficacy (positive and negative) as well as possible futility of further study will be examined at the interim analysis. Significance levels for the interim analysis will be altered by the method of Lan-DeMets. Safety will be evaluated at each meeting of the Data Safety and Monitoring Board.

*How will safety be evaluated and what study-specific stopping rules will be used by the DSMC?*

Safety will be evaluated by analyzing situations in which administration of the study drug is stopped according to the "STOPPING RULE" below.

The study would be stopped if nifedipine is found to significantly delay preterm birth, or if a significantly greater number of stillbirths or emergency deliveries due to nonreassuring fetal heart tracing attributable to study drug during the 48 hour period during which the study drug will be administered for acute tocolysis of preterm labor.

*What safety mechanisms are built into the Nifedipine study protocol?*

Apart from the strict inclusion and exclusion criteria and the plan to continue maternal and fetal monitoring for at least 24 hours after beginning the study, the following safety parameters are part of the study protocol:

There will be a "HOLD DOSE" parameter in which a dose will be held if an enrolled patient either refuses medication or has a heart rate greater than 120. If a dose is held, the nurse will contact the 4th year resident who will ensure [name] is notified.

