There will be a "STOPPING RULE" for further individual participation in the study for any of the following criteria: withdrawal of consent, diffuse rash or anaphylaxis reaction to medication (requires confirmation by house officer), hypotension requiring delivery or medication such as ephedrine, or development of any obstetrical outcomes that would normally preclude tocolysis

(development of ruptured membranes, development of chorioamnionitis, development of preeclampsia/gestational hypertension, development of bleeding suspicious for abruption, cervical dilatation of 6 cm or more or fetal death), or if a decision is made to either deliver the patient or to give regional anesthesia.

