Effective September 17, 2015, there has been a protocol change at the level of the Division of Maternal-Fetal Medicine at Parkland Hospital. This protocol change will be to give corticosteroids for fetal lung maturity to women with diabetes and to all women with hypertension who are at risk of preterm birth. This MFM Division level protocol change will affect this study of women at risk of preterm birth.

Given that 2 of the formerly ineligible women (due to diabetes) who presented in March 2015 would now be eligible due to the above protocol change, we estimate that up to 24 additional women (2 x 12 = 24) would be screened per year, and up to 12 additional women (50% of the 24 additional screened) would participate. Given that there were 29 women recruited over the initial 13 months (which equates to approximately 27 over 12 months), under the new practice in which corticosteroids will be given more broadly (and women with diabetes and mild hypertension not treated with medications are eligible for participation), we estimate that up to 78-90 women would now be screened, and of these, we estimate that 39-40 women would participate per year.

Therefore, over ~4-5 years, we would expect 300 patients screened and 150 patients consented. In order to detect a 33% reduction in the rate of preterm birth less than 37 weeks’ gestation, assuming 80% power and a 2-sided alpha of 5%, a sample size of 75 patients per arm (two arms, study drug and placebo), 150 patients total, will need to be recruited. So far in the current study, we have had about a 50% consent rate. Assuming a 50% recruiting rate (50% x 300 = 150), it is estimated that this study will take 4 to 5 years to complete.

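### Gestational hypertension that develops after randomisation ends participation as a condition that normally rules out tocolysis, but the entry criteria neither exclude it nor say whether it is covered by the eligibility of untreated mild hypertension.

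*Combined protocol and SAP*

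**What the plan says.** Four places bear on this point.

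- **Stopping rule (Section 4, item 1).** Further participation ends on "development of any obstetrical outcomes that would normally preclude tocolysis (development of ruptured membranes, development of chorioamnionitis, development of preeclampsia/gestational hypertension", followed by bleeding suggesting abruption, dilatation of 6 cm or more, and fetal death. The data safety monitoring summary in Section 11 repeats the rule, including "development of preeclampsia/gestational hypertension", and describes it as stopping administration of study drug.
- **Exclusions (Section 7).** The block headed Tocolysis contraindicated lists "Preeclampsia" and no other hypertensive disorder. The block headed Nifedipine contraindicated adds "Chronic hypertension treated with antihypertensives in pregnancy". Section 11, item 1 restates the exclusion as drug-treated hypertension, without the word chronic.
- **Eligibility after the September 2015 practice change (Section 14, item 2).** The plan states that "women with diabetes and mild hypertension not treated with medications are eligible for participation". It does not say whether this hypertension is chronic, gestational or either.
- **Risk narrative (Section 1, item 3 and the end of Section 10, item 1).** Both say that use will be restricted to women who are healthy and have normal blood pressure.

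**The concern.** The stopping rule gives its own reason: these are conditions in which tocolysis would ordinarily not be given. That reason describes the condition, not the time at which it began. One would therefore expect a woman who already has the condition at screening to be excluded, or the plan to say why she is handled differently. For gestational hypertension it does neither.

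This bears first on the safety of participants. The listed criteria admit women with a condition that the protocol itself says normally rules out the study treatment. It also bears on consistent conduct: staff screening a woman with untreated raised blood pressure have one section that admits her, two that describe a population without her, and a stopping rule that names what may be her diagnosis. Finally, the monitoring committee evaluates safety through stops under this rule, so it matters whether a recorded hypertension stop is new disease or disease present at entry.

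**Working it through.** The plan has no figure on this point, so the check is a comparison of texts.

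**Step 1. Match the stopping list to the exclusion list.**

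| Condition in the stopping rule (Sections 4 and 11) | Counterpart in Section 7 |
|---|---|
| Ruptured membranes | Yes |
| Chorioamnionitis | Yes |
| Preeclampsia | Yes |
| Gestational hypertension | **None** |
| Suspected abruption | Yes |
| Advanced dilatation (6 cm or more) | Yes, at a different threshold (more than 4 cm) |
| Fetal death | Yes |

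Six of seven have a counterpart. The stopping rule joins preeclampsia and gestational hypertension in a single term; the exclusion list carries only the first.

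**Step 2. Follow three women through the text.**

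- Untreated chronic mild hypertension at entry: not excluded by Section 7, eligible under Section 14, not named in the stopping rule. No conflict among the criteria, but she falls outside the population described in Sections 1 and 10.
- Untreated gestational hypertension at entry: not excluded by Section 7. Eligible under Section 14 if mild hypertension includes the gestational form, which is not stated. The stopping rule, read literally, does not reach her, because she did not develop the condition after enrolment. She stays on blinded study drug.
- Normal blood pressure at entry, gestational hypertension during treatment: the stopping rule applies and she stops.

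The second and third women have the same condition during treatment and are handled in opposite ways, with no reason given.

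**Step 3. Look for a size.** Three places could supply one.

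- *Sample size.* The 75 per arm follows from 71.2% v 47.5%, two-sided alpha 5% and 80% power with the continuity-corrected two-proportion formula; without the correction it is 67. Hypertension is not an input.
- *Accrual forecast.* The extra accrual in Section 14 is 2 women with diabetes per month × 12 = 24 screened, × 50% = 12 enrolled per year. Women with hypertension contribute nothing to it.
- *Screening sample.* Of 10 women in March 2015, 6 were ineligible. The itemised reasons are 2 + 1 + 1 + 1 = 5 (diabetes, twins, age 15, bleeding). None is hypertension, and one reason is not given.

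The documents therefore give no count of women with untreated or gestational hypertension, and no effect on power can be calculated from them.

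**The case against.** The best defence has four parts.

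1. *The stop is worded as development of the condition.* Onset after enrolment and status at entry are different things, so the rules need not meet in one woman. This stands.
2. *Mild untreated hypertension may mean chronic hypertension*, as the complement of the treated chronic hypertension excluded in Section 7. The reading is plausible, but the sentence does not contain that limit. Even if it did, Section 7 would still list nothing against untreated gestational hypertension at entry.
3. *Entry and stopping lists are not mirror images by design.* Dilatation has different thresholds before and after randomisation. Oligohydramnios, growth restriction and placenta previa are exclusions that the stopping rule does not name. So an unmatched item alone proves little. This stands, but here the plan also supplies the reason, that the condition normally rules out tocolysis, and the reason does not depend on timing.
4. *Sections 1 and 10 already restrict use to women with normal blood pressure.* These are statements in the risk discussion, not listed criteria, and Section 14 contradicts them. They add to what must be reconciled.

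A reader might go further and infer that eligible women would meet the stopping rule at the moment of randomisation, that the intent-to-treat comparison would be diluted and lose power, and that the committee's safety measure would be distorted. The documents do not support this. It requires setting aside the word development and also assuming that mild hypertension includes the gestational form. There is, besides, no count from which to compute a loss. On the literal reading, there are no immediate stops and hence no dilution from this source.

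**Conclusion.** The point holds as an inconsistency between the stated entry criteria and the stated stopping criteria, with a bearing on participant safety. It rests on two textual facts that are not open to interpretation: gestational hypertension is named as a condition that normally rules out tocolysis, and it is absent from the exclusions. The eligibility sentence in Section 14 and the restriction to normal blood pressure in Sections 1 and 10 make the intended population harder to establish.

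What remains open is whether mild hypertension in Section 14 includes gestational hypertension, and how the stopping rule is meant to treat a woman who already has it at entry. The number of women affected is unknown and may be small. No claim is made about power, bias in the primary comparison, or which clinical rule is correct.

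**What to change.** Reconcile the stopping rule (Section 4, item 1 and the monitoring summary in Section 11) with the exclusions in Section 7, the eligibility sentence in Section 14, item 2, and the population statements in Sections 1 and 10. Two statements are needed:

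- whether mild untreated hypertension in Section 14 includes gestational hypertension;
- how a woman who has gestational hypertension at entry is handled, worded so that the entry and stopping criteria agree for her.

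The content of both is a clinical decision for the investigators.

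In addition, record hypertension status (none, chronic, gestational; treated or not) at randomisation, so that the committee's review of stopped treatment can separate disease present at entry from new onset.

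The cost is a line or two in each affected section and one baseline item. If the condition becomes an exclusion, a few women may be lost from accrual. The forecast increase of up to 12 women per year is unaffected, because it is built on women with diabetes. The stated sample-size inputs do not change.

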## **5. Sub-Study Procedures:**

1. *For any sub-studies that may be a part of the research, please provide a subsection title and include information about the procedures that will be performed and whether subjects have the option to participate or not (e.g., pharmacokinetics, biomarkers).*

N/A

2. *For studies that collect blood and/or tissue for DNA analysis where the genetic portion is described in the Master Protocol provide a genetic subsection to include information about the procedures that will be performed and whether subjects have the option to participate in the sub-study.*

N/A

## **6. Criteria for Inclusion of Subjects:**

1. *Describe the characteristics of the subject population. For example, list any characteristics required for eligibility, such as diagnosis, prior therapy, age, or gender.*

Inclusion criteria include:

- Mothers between 16 and 44 years of age inclusive.
- Singleton pregnancy
- Intact membranes
- Between 28-0/7 weeks and 33-6/7 weeks' gestation inclusive
- Reported or documented uterine activity
- Cervical dilation between 2 cm and 4 cm inclusive

2. *Explain the rationale for the use of special classes of subjects who are more likely to be vulnerable, such as pregnant women, children, cognitively impaired people or prisoners.*

Pregnant women are included as this study is for an intervention for preterm labor.

## **7. Criteria for Exclusion of Subjects:**

1. *Describe the exclusion criteria. For example, list any characteristics that would preclude participation, such as prior therapy, concomitant treatments and co-morbid conditions. If exclusion is based on age, gender, language barriers or social/ethnic group, describe the need*

*for the exclusion in terms of scientific validity. Do not justify exclusion in terms of convenience or other non-scientific issues, such as lack of funding.*

**Exclusion criteria:**

Oppose inclusion criteria:

- Multifetal gestation
- Less than 28 weeks' gestation
- 34 or more weeks' gestation
- Ruptured membranes

• More than 4 cm dilated  
Corticosteroids contraindicated:

- Previously received a course of corticosteroids for fetal lung maturation

Tocolysis contraindicated:

- Low amniotic fluid (oligohydramnios)
- Fetal growth restriction
- Chorioamnionitis or temperature of at least 38.0 degrees Celsius
- Fetal death
- Preeclampsia
- Suspected placental abruption or placenta previa
- Lethal fetal malformation or amniotic fluid index at least 35

Nifedipine contraindicated:

- Systolic BP < 90 mmHg or diastolic BP < 50 mmHg
- Baseline tachycardia (pulse >120 after 2 consecutive measurements 30 minutes apart)
- Chronic hypertension treated with antihypertensives in pregnancy
- Seizure disorder or HIV\*
- Women who have received progesterone therapy in the 2nd or 3rd trimester
- Maternal allergy to nifedipine
- Known maternal cardiac disease

\* See July 2013 FDA warning regarding nifedipine and phenytoin, also several protease inhibitors are strong inhibitors of metabolizing enzyme CYP3A4

2. *Include situations or conditions, unknown at the time of enrollment that might cause a screening failure.*

No situations known.

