Given the prevalence of this off-label use of nifedipine, it is unlikely that serious adverse events are commonly encountered. The main serious risk associated with nifedipine is pulmonary edema, but in the 17 reported cases, this risk was reported in the context of other specific risk factors, such as use with other tocolytic drugs, use of rapid-acting formulations, prolonged tocolysis, and use when there was evidence of preexisting maternal cardiac disease/dysfunction. Importantly, in 26 published trials involving isolated use of nifedipine for acute tocolysis, there were no cases of pulmonary edema among patients receiving nifedipine (References 8a-aa).

We plan to restrict use to healthy, normotensive women with singleton pregnancies not receiving additional tocolytic agents. We will also **not** use prolonged or sublingual (rapid acting) administration of nifedipine. Therefore, these reported adverse reactions are most unlikely. Milder side effects associated with nifedipine include headache, flushing and low blood pressure, which resolve with discontinuation of the medication. The balance of benefits and risks favors performing this study to quantify benefits, if any, given the potential for nifedipine to stop preterm labor and its high use rate in the community.

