#### **4. Study Procedures:**

- 1. Provide a chronological description of all study procedures. If applicable, divide procedures into pilot, screening, and procedures performed at each regular visit. Indicate how many total visits and approximately how long visits will last. For studies that are providing medication(s), give the name(s), dosage, and route of administration. For studies that have more than one arm/part, provide the above information for each.*

Women presenting with symptoms of preterm labor will be assessed using electronic external fetal heart rate and uterine contraction monitoring. Women will receive a baseline and subsequent cervical exams as necessary. If at any time during her evaluation, the woman is dilated to at least 2 cm and has uterine contractions, she will be potentially eligible for study. Women with a singleton gestation between 28-0/7 weeks and 33-6/7 will be approached for consent to participate by Research Nurses employed by the Department of Obstetrics & Gynecology or [name] if a Research Nurse is unavailable. They will be randomized by the IDS Pharmacy into treatment (study drug, nifedipine) or control (placebo) groups.

Study women will receive nifedipine 20 mg or placebo oral capsule followed by a second dose after 90 minutes if there are persistent contractions. Four hours after the initial dose, they will begin nifedipine 20 mg or placebo oral capsule every 4 hours for a total duration of 48 hours, up to a maximum of 160 mg the first 24 hour period (120 mg the second 24 hour period), unless delivery occurs sooner. We anticipate that women will remain on Labor & Delivery for monitoring for at least 24 hours prior to consideration of transfer to the high-risk antepartum unit.

There will be a "HOLD DOSE" parameter in which a dose will be held if an enrolled patient:

- refuses medication
- has heart rate greater than 120

If a dose is held, the nurse will contact the 4th year resident who will ensure [name] is notified.

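### Seizure disorder and HIV are excluded only because of interacting drugs, but no criterion tests for the drugs themselves (minor safety mismatch, cheap to close)

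*Combined protocol and SAP*

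**What the plan says.** In Section 7 (Criteria for Exclusion of Subjects), the sub-list of reasons why nifedipine is contraindicated includes "Seizure disorder or HIV", marked with an asterisk. The footnote reads "See July 2013 FDA warning regarding nifedipine and phenytoin" and adds that "several protease inhibitors are strong inhibitors of metabolizing enzyme CYP3A4". It gives no other reason for either diagnosis.

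Two lines of the same sub-list already depend on medication use: "Chronic hypertension treated with antihypertensives in pregnancy" and "Women who have received progesterone therapy" (in the second or third trimester). The form's instruction at the head of Section 7 gives examples of what may be listed: "such as prior therapy, concomitant treatments and co-morbid conditions".

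On accompanying drugs, Section 1 (item 3) says: "We plan to restrict use to healthy, normotensive women with singleton pregnancies not receiving additional tocolytic agents". Section 10 repeats this. Dosing in Section 4 is 20 mg by mouth, repeated at 90 minutes if contractions persist, then 20 mg every four hours to 48 hours, "up to a maximum of 160 mg the first 24 hour period" and 120 mg in the second.

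**The concern.** The hazard named in the footnote is a drug; the criterion tests a diagnosis. The diagnosis is an easy proxy, and it catches every woman who has either condition. It does not catch a woman who takes phenytoin, or a drug that strongly inhibits CYP3A4, for another reason. She would be enrolled under the written rules, although the footnote shows that the sponsor wanted to avoid the combination.

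What is at stake is individual safety, not the trial's answer. The footnote calls CYP3A4 a metabolizing enzyme, so strong inhibition points to slower clearance and higher nifedipine exposure under the full dosing schedule. The documents do not say how much higher. For phenytoin they cite a warning without its content, so they support neither a direction nor a harm.

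**Working it through.** The plan gives no figure on this point, so there is none to reproduce. The check has two parts: whether any other rule screens for the drugs, and what closing the gap would cost.

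**1. Does another rule screen for these drugs?**

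| Place | What it restricts | Screens for phenytoin or CYP3A4 inhibitors? |
|---|---|---|
| Section 6, inclusion criteria | Age, singleton, intact membranes, gestation, uterine activity, dilation | No |
| Section 7, medication-based lines | Prior corticosteroid course, antihypertensives for chronic hypertension, progesterone | No |
| Sections 1, 2 (Safety), 10 and 11, accompanying drugs | Other tocolytics | No |
| Sections 10 and 11, magnesium sulfate | Avoided; Section 11 does so through the 28-week lower limit | No |
| Section 11, restated exclusions | Hypotension, tachycardia, cardiac disease, treated hypertension | No |
| Sections 4 and 11, hold-dose rule | Refusal; heart rate above 120 | No |
| Sections 4 and 11, individual stopping rule | Consent withdrawal, rash or anaphylaxis, hypotension needing delivery or medication, obstetric events, decision to deliver, regional anesthesia | No |

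None asks about the drugs. The last two act after dosing has begun and respond to effects, whatever their cause.

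**2. What would an added criterion cost?**

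Inputs from Section 14: target 150 women; 29 recruited in the first 13 months; 39 to 40 participants expected per year. The share *f* of otherwise enrollable women who take such a drug is not in the documents. I assume 0 to 2%.

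- Still to recruit from that count, as an upper bound: 150 − 29 = 121.
- Women excluded while reaching 121: 121/(1 − *f*) − 121.
- Extra accrual time at the lower rate: excluded ÷ 39 × 365 days.

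| Assumed *f* | Women excluded | Extra days |
|---|---|---|
| 0% | 0 | 0 |
| 0.5% | 121/0.995 − 121 = 0.6 | 6 |
| 1% | 121/0.99 − 121 = 1.2 | 11 |
| 2% | 121/0.98 − 121 = 2.5 | 23 |

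These figures bound the cost of the fix. They do not measure how many women are at risk or how likely harm is, and the documents allow neither to be computed.

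**The case against.** The strongest case for leaving the criterion alone is that nobody is shown to fall through it. For the drugs the footnote actually names, the gap needs a woman on phenytoin without a seizure disorder, or on a protease inhibitor without HIV. The documents give no sign that either occurs here. Reaching further, to strong CYP3A4 inhibitors in general, is an inference from the footnote's mechanism and not from any drug list in the plan. A diagnosis is also a simple screen for research nurses on Labor & Delivery, and it works when the drug history is incomplete. The form offers accompanying treatments only as an example, so listing them is not required. All of this stands. It keeps the point small and is a good reason to retain both diagnoses.

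The safeguards also count. Women with systolic pressure below 90, diastolic below 50 or a sustained pulse above 120 are excluded at baseline. Doses are held above 120 beats per minute, and participation stops for hypotension needing delivery or medication. Vital signs are monitored on both units, physicians are immediately available, and treatment ends at 48 hours. Section 10 cites a review in which nifedipine was discontinued for hypotension in 3 of 203 women (1.5%), and a study of normotensive pregnant women that found no significant clinical symptoms from hypotension. These limit the consequence but do not replace screening. The hold rule has no blood-pressure trigger, and neither data set isolates women on interacting drugs.

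It may be said that the word *healthy* in Sections 1, 2 and 10 closes the gap. It gives staff grounds to decline such a woman, but it describes the population and is not a criterion that can be checked. Section 14 also admits women with diabetes or untreated mild hypertension.

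**Conclusion.** The mismatch is real and minor. As written, the rule admits the exposure that its footnote was meant to avoid, and no other rule screens for it. Correcting it is an inexpensive improvement, with a small possible gain in individual safety.

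Three limits apply. The number of women affected is unknown and may be zero. A direction of concern is supported only for CYP3A4 inhibition; the phenytoin half is a mismatch with the footnote and no more. Covering strong inhibitors other than protease inhibitors rests on the footnote's mechanism.

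A reader might infer that participants face a demonstrated hazard, or that the trial's result is compromised. The documents support neither. They give no frequency of use, no size of interaction and no adverse event linked to these drugs in trial participants. The sample size and the primary comparison of preterm birth before 37 weeks do not depend on this line.

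**What to change.** Keep both diagnoses. In the Section 7 sub-list on nifedipine contraindications, add: *current use of phenytoin or of a strong CYP3A4 inhibitor (including protease inhibitors)*. Check it against the medication list before randomisation, together with the antihypertensive and progesterone criteria, which already need a medication history.

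The cost is a short eligibility amendment during recruitment, one more item in an existing check, and the occasional loss of an otherwise eligible woman within the range worked out above. Amending eligibility mid-trial is not new here: Section 14 records that it was widened for women with diabetes and untreated mild hypertension.
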